8.1.4.1 AzBio Sentence Testing in Quiet – AutoSound on the Q90 processor

AzBio Sentence Test in quiet will be administered at 65 dBA at 0° azimuth using the AutoSound program on the Q90 research processor. Two lists will be presented and the total number of words per list and words correct will be recorded for each list.

8.1.4.2 Moderate Open-Set Speech Recognition Criteria

Subjects who do not meet at least moderate open-set speech recognition criteria with the implant alone as defined by a minimum score of 60% in the Naída CI Q90 AzBio Sentence Testing in Quiet will be considered baseline failures and will be exited from the study.

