6.2 Study Endpoints

6.2.1 *Efficacy*

The purpose of the proposed study is to evaluate efficacy objectives. Speech performance and subjective outcome data will be collected during the study. The primary efficacy endpoints are the AzBio sentence scores in quiet at Baseline with AutoSense on a M90 processor as compared to AzBio sentence scores in quiet at Baseline with currently approved software on a Q90 processor. Secondary endpoints include:

- AzBio sentence scores in noise at Baseline with AutoSense on a M90 processor as compared to AzBio sentence scores in noise at Baseline with currently approved software on a Q90 processor.
- AzBio sentence scores in noise at Baseline with AutoSense on a M90 processor as compared to AzBio sentence scores in noise at Baseline with a manual “Omnidirectional” program on a M90 processor.

6.2.2 *Safety*

Adverse event data will be collected and evaluated during the study to ensure that the safety of patients is maintained as per requirements of an IDE and respective center Institutional Review Board guidelines for reporting. The primary safety endpoint is the absence of unanticipated adverse device effects related to use of AutoSense on a M90 processor.

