6.4 Inclusion and Exclusion Criteria

6.4.1 General Inclusion Criteria

- Ability to provide Informed Consent
- 18 years of age or older
- Unilateral user of a HiResolution™ Bionic Ear System (HiRes 90K™, HiRes 90K™ Advantage, HiRes™ Ultra, HiRes™ Ultra 3D), including bilaterally implanted subjects that only use one implant in their everyday listening modality
- Minimum of 6 months of CI experience
- Having used a Naída CI Q70 or a Naída CI Q90 as their primary processor for a minimum of one month
- Presently using a current steering strategy
- At least moderate open-set speech recognition abilities with implant alone, as defined by achieving a score of $\geq 60\%$ words correct in the AzBio in quiet test using the Naída CI Q90 research processor
- English language proficiency as determined by the investigator
- Willingness to use a BTE processor for the duration of the study

6.4.2 Inclusion Criteria ARH Cohort:

- Residual low frequency hearing sensitivity (pure tone average of < 70 dB HL for 125, 250, and 500 Hz) and a severe-to-profound high-frequency sensorineural hearing loss (pure tone average of ≥ 70 dB HL for 1,000, 2,000, 3,000, 4,000, and 8,000 Hz) in the implanted ear
- Willingness to use an in-canal acoustic earhook for the duration of the study

6.4.3 Inclusion Criteria EO Cohort:

- Severe-to-profound sensorineural hearing loss in the low (pure tone average of ≥ 70 dB HL for 125, 250, and 500 Hz) and high frequencies (pure tone average ≥ 70 dB HL for 1,000, 2,000, 3,000, 4,000, and 8,000 Hz) in the implanted ear

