8.1.5 Naída CI M90 Fitting

Subjects will be fitted with a M90 investigational processor with a M90 T-mic (EO cohort) or a M90 acoustic earhook with a dome (ARH cohort) using the investigational Target CI software wirelessly through NoahLink or with the Clinicians Programming Interface (CPI-3). Strategy, M and T levels, IDR, ClearVoice, SoftVoice and filter settings will be the same as on the Q90 research processor, within the constraints of the fitting software. AutoSense presets in the automatic program will remain unchanged from the pre-defined settings for the AutoSense testing. For the ARH cohort, the M90 research processor will be programmed to have the processor microphone selected. Acoustic and electric cutoff frequencies for subjects in the ARH cohort should approximate those from Q90 research processor. If a match is not available in Target CI, a similar and subjectively acceptable cutoff frequency should be chosen. In addition, a manual “Omnidirectional” program will be created using the “Calm Situation” scene with the Omni microphone mode and the applicable FEPs at the “OFF” settings [REDACTED].

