8.1.6 AutoSense Speech Perception Testing

8.1.6.1 AzBio Sentence Testing in Quiet – AutoSense on the M90 processor

The AzBio Sentence Test in quiet will be administered at 65 dBA at 0° azimuth using the AutoSense automatic program. Two lists will be presented and the total number of words per list and words correct will be recorded for each list.

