8.3 Summary of Visit Activities

Procedure	Baseline Visit		Chronic Period
	EO Cohort	ARH Cohort	
Informed Consent	✓	✓	
Demographics & Audiological History	✓	✓	
Audiometric Thresholds	✓	✓	
Confirmation of Eligibility	✓	✓	
Custom Self-Assessment Questionnaire	✓	✓	✓
AutoSound on the Q90 Processor	AzBio in Quiet	✓	✓
	AzBio in Noise	✓	✓
AutoSense on the M90 Processor	AzBio in Quiet	✓	✓
	AzBio in Noise	✓	✓
“Omnidirectional” program on the M90 Processor	AzBio in Noise	✓	✓
Adverse Event Assessment	✓	✓	✓
Device Accountability	✓	✓	✓

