9.1.1 Data Analyses

9.1.1.1 Efficacy Endpoints

The primary efficacy endpoint is speech recognition on AzBio in quiet mode for AutoSense on the M90 processor vs AutoSound on the Q90 processor. Non-inferiority analyses will be based on paired t-tests looking at the differences in scores calculated using the Experimental results minus the Control scores at the baseline visit. A one-sided hypothesis test will be used with 0.05α for the primary efficacy evaluation evaluating the following hypothesis:

$$H_0: \mu_{\Delta} \leq -0.10 \text{ versus } H_1: \mu_{\Delta} > -0.10$$

where μ_{Δ} is the mean of the difference (AutoSense on M90 – AutoSound on Q90) on the AzBio sentence test in quiet. A non-inferiority bound of 0.10 (10%) was selected for the AzBio test based on procedures used in previous studies [REDACTED]

[REDACTED] Statistically significant test results that reject the null hypotheses, indicating that the means of the paired differences are greater than -0.1 (-10%) for AzBio in quiet mode, which will support that the Investigational condition is non-inferior to the Control condition.

The primary and secondary efficacy endpoints will be first considered for non-inferiority and then for superiority. The superiority tests are penalty-free since the alternative hypothesis for superiority is nested within the alternative hypothesis for non-inferiority. The superiority test will use one-sided $p=0.025$.

Additional analyses will be conducted to assess any differences based on age of onset or duration of sensorineural hearing loss (SNHL). An analysis of variance (ANOVA) will be used to model the paired differences (Investigational – Control) of AzBio sentences in quiet age of onset and duration of SNHL as the covariate. The analysis will be repeated for AzBio sentences in noise as well as for sentence recognition. The results will also be presented by age of onset and duration of SNHL.

Because the study includes a single visit followed by a chronic period with a subjective questionnaire, the possibility exists that some study participants will not complete the entire test protocol. Given the study design, no data will be imputed but efficacy analysis for other primary and secondary effectiveness endpoints will be repeated for the subset with missing data. In addition, to accommodate potential losses, additional subjects will be enrolled beyond the required sample size per cohort. Efficacy data will not be combined across cohorts.

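### The only scheduled Q90 quiet test is both the 60% entry gate and the primary control score, and M90 appears to be tested after it in everyone, so a test-order effect would count as a device effect

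*Combined protocol and SAP*

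**What the plan says.** - **Entry gate.** Section 6.4.1 requires at least 60% "words correct in the AzBio in quiet test" with the Q90 research processor. Section 8.1.4.2 applies this to the Q90 quiet test, and those who fall short "will be considered baseline failures and will be exited from the study".
- **The test.** Section 8.1.4.1 describes two quiet lists "using the AutoSound program on the Q90 research processor". The table in 8.3 has one AzBio-in-quiet entry under "AutoSound on the Q90 Processor" and no separate screening list.
- **The endpoint.** The primary endpoint in 6.2.1 is the M90 quiet score "as compared to AzBio sentence scores in quiet at Baseline with currently approved software on a Q90 processor".
- **The sequence.** The sections run in this order: Q90 fitting (8.1.3), Q90 quiet, gate, Q90 noise (8.1.4.1 to 8.1.4.3), M90 fitting (8.1.5), M90 quiet (8.1.6.1). The M90 settings "will be the same as on the Q90 research processor, within the constraints of the fitting software". The M90 quiet test is then given "using the AutoSense automatic program. Two lists will be presented".
- **The analysis.** Section 9.1.1.1 states: "Non-inferiority analyses will be based on paired t-tests looking at the differences in scores", taken as M90 minus Q90, with a superiority test to follow. The visible text has no randomised or counterbalanced order and no order term.

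**The concern.** In a within-subject comparison at one visit, the second test can gain from practice or lose from fatigue. If Q90 always comes first, device and test position are the same variable, and no analysis can separate them once the data are in. The within-subject rationale in 6.1 is heterogeneity between subjects, which does not address order.

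Let b be the points that M90 gains from being tested second (negative for a loss). The non-inferiority test then rules out a true deficit of 10 + b points, not 10. The superiority test has the same bias at true equality, which is close to the outcome that section 3.0 expects. This concerns the primary endpoint in both cohorts.

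A smaller issue runs the other way. Selecting subjects on the control score keeps those whose Q90 result was high partly by chance, which works against M90.

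**Working it through.** **Inputs from the documents.** Margin 10 points (9.1.1.1); one-sided alpha 0.025 per cohort (9.1.1.2); paired SD 6.24, 8 complete pairs out of 12 enrolled, and stated power 94% (9.1.2, Table 4); between-list SD 3.8 (9.1.1.3). **Assumed:** b, and the score distributions used for the selection effect.

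**1. The plan's own power.** Noncentrality = √n × 10 / SD = √8 × 10 / 6.24 = 4.53, df 7, critical t 2.365. Power is 97.1%, against 94% in Table 4. The stated figure does not reproduce from its stated inputs. That is a separate matter; the recomputed value is the reference below. With 12 pairs, power is 99.9%.

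**2. Fixed order, gain from being second.** At a true difference of −10, noncentrality = √n × b / SD. For b = 2 and n = 8 this is √8 × 2 / 6.24 = 0.907, giving 12.1%. The same rates apply to false superiority at a true difference of 0.

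| b (assumed) | 8 pairs | 12 pairs |
|---|---|---|
| 0 | 2.5% | 2.5% |
| +1 | 5.9% | 7.3% |
| +2 | 12.1% | 17.2% |
| +3 | 21.7% | 33.0% |

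**3. Fixed order, loss from being second.** Non-inferiority power at true equality, noncentrality = √n × (10 + b) / SD. For b = −2 and n = 8 this is √8 × 8 / 6.24 = 3.63, giving 87.3%.

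| b (assumed) | 8 pairs | 12 pairs |
|---|---|---|
| 0 | 97.1% | 99.9% |
| −1 | 93.6% | 99.5% |
| −2 | 87.3% | 98.1% |
| −3 | 77.6% | 94.2% |

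**4. Selection on the control score.** The expected error in a Q90 score that passed the gate is (se² / so) × φ(z) / (1 − Φ(z)), where so = √(st² + se²) and z = (60 − mean) / so. Here st is the between-subject SD and se the error SD. For an assumed mean of 65, st = 10 and se = 6.24/√2 = 4.41: so = 10.93, z = −0.457, and the shift is 0.95 points against M90. For a mean of 85, st = 10 and se = 3.8/√2 = 2.69, it is 0.02. The range is about 0 to 1 point.

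**5. Balanced order.** The order-adjusted estimate is the mean of the two order-group means, with SE = SD × √((1/n1 + 1/n2)/4) and df = n − 2. Power at true equality:
- 6:6: SE 1.80, power 99.9%.
- 4:4: SE 2.21, power 96.2%.
- 6:2: SE 2.55, power 90.2%.

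In simulation with equal groups (4:4 or 6:6), false non-inferiority for b = +1 to +3 was 1.6% to 2.4% with the planned paired t-test and about 2.5% with an order term.

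**The case against.** **The order is inferred.** A reader might take the plan to state that Q90 is tested first. No visible sentence does. The order follows from the section sequence and from the exit rule, which does not name the moment of exit. Figure 2 (section 7.2) is not shown and 8.1.4 is partly redacted, so an order rule out of sight cannot be excluded. This stands and limits the claim. Even so, a rule allowing M90 first in quiet would have to be squared with a gate that uses the only Q90 quiet test and is placed before M90 fitting.

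**The gate is not the whole cause.** A reader might infer that the gate forces the order. It does not: 6.4.1 asks for a score with the Q90 research processor, which a separate list could supply. The fixed visit sequence is the other cause, so extra lists alone would not balance the order.

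**Size and sign are unknown.** A reader might conclude that the plan favours M90. The documents do not support that. Practice would favour M90, while fatigue and selection on the control score would work against it. At the top of its assumed range, selection would nearly cancel b = +1. Subjects also have at least a month on a Q70 or Q90 (6.4.1) and are tested on M90 acutely. All this stands, so the tables are sensitivity figures, not estimates of bias.

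**It is a design choice.** A fixed order confirms eligibility before investigational fitting. A separate screening list placed before M90 fitting keeps that advantage.

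**Noise.** A reader might extend the point to the three noise conditions. The visible text gives no order rule for them, and with the flow chart missing no error is claimed there.

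**Conclusion.** The point holds as a design weakness that should be corrected, with medium confidence. On the visible text, one Q90 quiet score is both gate and primary control, and the natural reading puts M90 second for every subject. An order effect would then be inseparable from the device effect in the primary test and in the superiority test. Superiority is the more exposed claim, because similar performance is the expected case.

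The effect could be negligible or material. False-positive rates double to 5% at b of about 0.8 points (8 pairs) or 0.6 points (12 pairs), but the documents give no value for b. The figures hold the paired SD at 6.24 and treat b as the same for every subject.

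**What to change.** 1. Decide the unchanged 60% gate on one or two separate Q90 quiet lists not used in any endpoint. State that a subject who passes stays in the analysis whatever the later scored Q90 result. State whether the gate uses one list or two. Reconcile the implant-alone wording of 6.4.1 and 8.1.4.2 with 8.1.3, where the ARH cohort's Q90 program has the acoustic mode switched on.
2. Fit the M90 after the gate.
3. Run the scored tests in two blocks, one per device, with block order drawn from a central pre-generated list balanced within cohort (6 and 6).
4. Keep the paired t-test as the planned test, record the order, and add an order-adjusted sensitivity analysis. If losses left a 6:2 split with Q90 first in six (probability 15/495 = 3% for a random 8 of 12), unadjusted false non-inferiority at b = +2 would be 5.1%.
5. If Figure 2 or the redacted text already sets a balanced order, state it in 8.1 and reconcile it with the gate.

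**Cost.** Lists per subject rise from 10 (five conditions × 2) to 11 or 12, with one or two extra processor swaps during testing and some added listening load. The sponsor must check that enough unused lists exist and arrange central order assignment. No extra subjects are needed. A one-list gate is less precise: error SD 3.8/√2 = 2.7 points, against 3.8/2 = 1.9 with two.

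**What remains.** Unequal carry-over is not removed. The Q90 block has four scored lists and the M90 block six, so the two orders are not perfectly symmetric. The screening lists also give a little extra Q90 listening, though before both scored blocks.

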8.1.4.3 AzBio Sentence Testing in Noise – AutoSound on the Q90 processor

The AzBio Sentence Test in noise will be administered at 65 dBA + 5 dB SNR Multi-Talker-Babble (MTB) with speech presented at 0° azimuth and noise presented at 180° azimuth using the AutoSound program on the Q90 research processor. Two lists will be presented and the total number of words per list and words correct will be recorded for each list.

8.1.5 Naída CI M90 Fitting

Subjects will be fitted with a M90 investigational processor with a M90 T-mic (EO cohort) or a M90 acoustic earhook with a dome (ARH cohort) using the investigational Target CI software wirelessly through NoahLink or with the Clinicians Programming Interface (CPI-3). Strategy, M and T levels, IDR, ClearVoice, SoftVoice and filter settings will be the same as on the Q90 research processor, within the constraints of the fitting software. AutoSense presets in the automatic program will remain unchanged from the pre-defined settings for the AutoSense testing. For the ARH cohort, the M90 research processor will be programmed to have the processor microphone selected. Acoustic and electric cutoff frequencies for subjects in the ARH cohort should approximate those from Q90 research processor. If a match is not available in Target CI, a similar and subjectively acceptable cutoff frequency should be chosen. In addition, a manual “Omnidirectional” program will be created using the “Calm Situation” scene with the Omni microphone mode and the applicable FEPs at the “OFF” settings [REDACTED].

8.1.6 AutoSense Speech Perception Testing

8.1.6.1 AzBio Sentence Testing in Quiet – AutoSense on the M90 processor

The AzBio Sentence Test in quiet will be administered at 65 dBA at 0° azimuth using the AutoSense automatic program. Two lists will be presented and the total number of words per list and words correct will be recorded for each list.

8.1.6.2 AzBio Sentence Testing in Noise – AutoSense on the M90 processor

The AzBio Sentence Test in noise will be administered at 65 dBA + 5 dB SNR Multi-Talker-Babble (MTB) with speech presented at 0° azimuth and noise presented at 180° azimuth using the AutoSense automatic program. Two lists will be presented and the total number of words per list and words correct will be recorded for each list.

8.1.7 “Omnidirectional” Speech Perception Testing

The AzBio Sentence Test in noise will be administered at 65 dBA + 5 dB SNR Multi-Talker-Babble (MTB) with speech presented at 0° azimuth and noise presented at 180° azimuth using the “Omnidirectional” manual program. Two lists will be presented and the total number of words per list and words correct will be recorded for each list.

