Evaluation of AutoSense OS on a Naída CI M90 Sound Processor Programmed with Target CI Fitting Software in Adult Users of the HiResolution Bionic Ear System

	ear
Exclusion Criteria All Cohorts	
 • Unrealistic expectations regarding potential benefits, risks and limitations of the investigational device as determined by the investigator • Unwillingness or physical / cognitive inability of subject to comply with all investigational requirements as determined by the investigator
Primary Efficacy Objective	The primary efficacy objective is to demonstrate that speech recognition in quiet with AutoSense on a M90 processor is no worse than speech recognition in quiet with currently approved software on a Q90 processor.
Secondary Efficacy Objective(s)	
The secondary efficacy objectives are
 
 • To demonstrate that speech recognition in noise with AutoSense on a M90 processor is no worse than speech recognition in noise with currently approved software on a Q90 processor. • To demonstrate increased speech recognition in noise with the M90 sound processor when comparing “Omnidirectional” program to AutoSense
Safety Objective	The primary safety objective is to evaluate whether there are adverse events related to the use of AutoSense on a M90 processor that impact device safety.
Primary Efficacy Endpoint	AzBio sentence scores in quiet at Baseline with AutoSense on a M90 processor as compared to AzBio sentence scores in quiet at Baseline with currently approved software on a Q90 processor
Secondary Efficacy Endpoint(s)	
 • AzBio sentence scores in noise at Baseline with AutoSense on a M90 processor as compared to AzBio sentence scores in noise at Baseline with currently approved software on a Q90 processor. • AzBio sentence scores in noise at Baseline with AutoSense on a M90 processor as compared to AzBio sentence scores in noise at Baseline with a manual “Omnidirectional” program on a M90 processor.
Safety Endpoint	Absence of unanticipated adverse device effects related to use of AutoSense on a M90 processor
Supporting Data	Analysis of non-standardized subject questionnaire after two weeks of use of AutoSense OS and a M90 processor in everyday listening situations.
Study Monitoring	Advanced Bionics, LLC [name] [REDACTED]

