6.0 Study Protocol

6.1 Study Design and Justification

This study uses a prospective within-subjects repeated-measures design. A within-subject repeated-measures study design is appropriate as it accommodates the heterogeneity that characterizes hearing-impaired populations. Acute speech performance testing will be used to evaluate AutoSense programmed on a M90 processor using Target CI fitting software (investigational device) as compared to approved software on a Q90 processor using SoundWave fitting software (control device). In addition, speech performance will be tested with a manual “Omnidirectional” program on a M90 processor. Statistical analyses will be used to determine if sentence perception with the investigational device is no worse than with the control device, confirmation of the non-inferiority hypothesis. A chronic exposure period of two weeks will be used to evaluate the investigational device in the subjects everyday hearing environment.

Adverse events (AEs) will be tracked and reported to the FDA according to the requirements of an IDE investigation until the study is closed. The AEs will be recorded and tracked between completion of the informed consent form and two weeks after the participant completes the study.

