8.2 Chronic Period

8.2.1 Chronic Period Instructions

Prior to starting the chronic period, the “Omnidirectional” program will be deleted from the M90 processor and subjects will exclusively use AutoSense on the investigational M90 processor with a T-mic (EO cohort) or an acoustic earhook with a dome (ARH cohort) for 14-21 days during their everyday activities. Slight adjustments may be made to the programming, as needed.

Once the subject has returned the processor to the study site, the Investigator will connect the processor to the Target CI fitting software and create a session to document the chronic use period.

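### On the readable text, AutoSense always precedes Omnidirectional in the M90 noise tests, so any order effect is confounded with the second secondary endpoint

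*Combined protocol and SAP*

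**What the plan says.** Section 6.1 gives the design: "This study uses a prospective within-subjects repeated-measures design". Section 8 then lists the baseline tests in one sequence, each with two AzBio lists: Q90 AutoSound in quiet (8.1.4.1), Q90 AutoSound in noise (8.1.4.3), M90 AutoSense in quiet (8.1.6.1), M90 AutoSense in noise (8.1.6.2), and finally "8.1.7 “Omnidirectional” Speech Perception Testing", which is in noise only. The visit table in 8.3 has the same order.

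Both M90 programs exist before any M90 test. Section 8.1.5, on the M90 fitting, states: "In addition, a manual “Omnidirectional” program will be created using the “Calm Situation” scene with the Omni microphone mode". The comparator stays on the processor until the take-home period, when according to 8.2.1 the Omnidirectional "program will be deleted from the M90 processor and subjects will exclusively use AutoSense on the investigational M90 processor".

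The synopsis gives the objective for this pair as an increase: "To demonstrate increased speech recognition in noise with the M90 sound processor", comparing Omnidirectional with AutoSense. Section 9.1.1.1 specifies paired t-tests, with superiority at one-sided 0.025. Section 9.1.1.2 tests the endpoints hierarchically within each cohort, and this comparison comes third.

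**The concern.** A within-subject comparison removes differences between subjects but not differences between early and late testing. If every subject takes Omnidirectional after AutoSense, program and test position cannot be separated by any analysis of the data. The paired difference then estimates the program effect plus the order effect. Because the aim is to show an increase, a decline over the session pushes towards the claim. Improvement with practice pushes against it.

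The order of these two tests also appears to be unforced. The Q90 quiet test has to come early because subjects scoring below 60% "will be considered baseline failures and will be exited from the study". That rule places no constraint on two programs that sit on the same M90. For the same reason, the subject need not be told which program is running, which is harder to arrange for Q90 against M90.

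**Working it through.** **List positions.** Five conditions × 2 lists = 10 lists. Q90 quiet is 1-2, Q90 noise 3-4, AutoSense quiet 5-6, AutoSense noise 7-8, Omnidirectional noise 9-10. The two compared blocks are adjacent.

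**The plan's own figures.** Section 9.1.2 and Table 4 give power of 94% and 90% for non-inferiority of M90 to Q90 in quiet and in noise (8 pairs, one-sided 0.025, SD 6.24 and 6.61). The noncentral t gives 97.1% and 95.4% from those inputs. The gap does not affect this point. Neither power nor an SD is given for AutoSense against Omnidirectional.

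**Inputs for the illustration.**
- SD of the paired difference: 6.61 points, borrowed from M90 vs Q90 in noise (9.1.2); range 5 to 10 assumed.
- True program effect: 0. Order effect against the later block: b = 2 points, assumed.
- One-sided α = 0.025 (9.1.1.1, 9.1.1.2); n = 12 enrolled or 8 complete pairs (9.1.2).

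**Case 1: the drop falls only on the last block.** The false superiority rate is P(T > t(0.975, n−1)), where T is noncentral t with n−1 degrees of freedom and noncentrality b√n/SD.
- n = 12: 2 × √12 / 6.61 = 1.05, rate 15.8%.
- n = 8: 2 × √8 / 6.61 = 0.86, rate 11.2%.

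| SD | n = 12 | n = 8 |
|---|---|---|
| 5 | 24.4% | 16.4% |
| 6.61 | 15.8% | 11.2% |
| 10 | 9.2% | 7.1% |

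The observed mean needed for significance at SD 6.61 is t(0.975, n−1) × 6.61/√n: 4.20 points with 12 pairs and 5.53 with 8.

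**Case 2: the same drop per block throughout the session.** Each M90 vs Q90 comparison spans two blocks, so AutoSense loses 2b in both earlier endpoints and gains b in the third. I simulated the full sequence: pass both non-inferiority tests at −10, then reach superiority. There were no true differences, the SDs were 6.24 (quiet) and 6.61 (both noise pairs), and the AutoSense noise score was shared between the second and third tests with equal independent error per condition.

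| Drop per block | n = 12: pass both gates | n = 12: pass and falsely superior | n = 8: pass both gates | n = 8: pass and falsely superior |
|---|---|---|---|---|
| 2 | 70% | 13% | 39% | 6% |
| 3 | 25% | 11% | 11% | 4% |
| 5 | 0.06% | 0.06% | 0.07% | 0.06% |

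**Case 3: practice instead of fatigue.** A 2-point gain on the later block cuts the rate to 0.2% (n = 12) or 0.3% (n = 8) at SD 6.61. The test is then conservative and a true benefit is understated.

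**Balanced order.** With half of each cohort in each block order and a 2-point order effect, simulation of the ordinary paired t-test gives 2.1% at both sample sizes.

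**The case against.** **The order is inferred.** No sentence makes the section sequence mandatory. Parts of 8.1.4 (test administration) and the end of 8.1.5 are redacted, and the flow chart in 7.2 is not shown. A rule on order or masking may be there. This stands, and it limits the point to the readable text. Sections 6.1, 8.1.6 and 8.1.7 show no redaction and contain no such rule.

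**The blocks are adjacent.** A reader might infer from Omnidirectional being last of ten lists that a fresh subject is compared with a tired one. The documents do not support that: AutoSense in noise also follows the audiogram, both fittings and six lists. The contrast is lists 7-8 against 9-10, so the drop between them may be small.

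**The hierarchy protects against large drifts.** A reader might carry Case 1 up to a 5-point drop and quote false superiority rates of 67% (n = 12) or 45% (n = 8). Those hold only if fatigue is absent for eight lists and then costs 5 points at once. Steady fatigue of that size fails the earlier tests almost always. The objection stands for large drifts; at 2 to 3 points per block some inflation remains.

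**The direction is unknown.** Subjects have just been fitted with an unfamiliar processor, so adaptation could favour the later lists. This also stands, but it does not remove the confounding: the estimate is biased either way.

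**Conclusion.** The point holds as a cheap improvement. On the readable text, program and test position are fully confounded for the second secondary endpoint in both cohorts, and the analysis has no term that could separate them. For a 2-point decline, the false superiority rate is about 16% (12 pairs) or 11% (8 pairs) if the decline is confined to the last block, and about 13% or 6% if it is steady and the hierarchy is applied, against 2.5% nominal. These figures rest on an assumed decline and a borrowed SD; they illustrate sensitivity and do not predict the result. If the true benefit is large, significance may not change, but the estimated size would still carry the order effect.

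A reader might also conclude that the trial is known to be unmasked, or that its claim is biased in favour of AutoSense. The documents support neither: masking is only not described in the readable text, and the sign of any order effect is not known.

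**What to change.** In 8.1.6.2 and 8.1.7, present the four M90 noise lists as AutoSense-Omni-Omni-AutoSense for half of each cohort and as Omni-AutoSense-AutoSense-Omni for the other half, assigned from a short randomisation list. Do not tell the subject which program is active. Keep the paired analysis on the mean of the two lists per program. Both programs then have mean position (7 + 10)/2 = (8 + 9)/2 = 8.5, so a linear drift, or a drop between lists 8 and 9, cancels within each subject. If a rule on order or masking already exists in the redacted text or the flow chart, state it in these two sections.

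The cost is protocol wording, an allocation list and a few extra program switches, with the same lists and visit. There is one statistical cost. The AutoSense noise lists also serve the first secondary endpoint, and their mean position moves from 7.5 to 8.5, while the Q90 noise lists stay at 3.5. Under a steady drift of 2 points per block (1 per list), the drift against AutoSense in that comparison would grow from 4 to 5 points.
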